## **5. Subject population**

The subjects of this study were patients with post-stroke consciousness disorder.

### **5.1 diagnostic criteria**

(1) Patients diagnosed with cerebral hemorrhage and cerebral infarction according to the Chinese Guidelines for the Diagnosis and Treatment of Cerebral Hemorrhage 2019 and the Chinese Guidelines for the Diagnosis and Treatment of Acute Ischemic Stroke 2018 authored by the Neurology Branch of the Chinese Medical Association;

(2) Disturbance of consciousness dominated by altered degree of arousal: refer to the patients diagnosed as disturbance of consciousness in the 8th edition diagnostic criteria of Neurology, the textbook of the 13th Five-Year Plan of the National Health Commission in 2018.

### **5.2 inclusion criteria:**

(1) sign the informed consent voluntarily;

(2) met the above diagnostic criteria, and the GCS score was between 3 and 9 (the score was scored by a rehabilitation physician, and the patient had not used sedatives or anesthetics on the day of the score);

- (3) The patient's condition is stable, vital signs are stable, and the onset time of consciousness disturbance caused by stroke is confirmed to be less than 6 months;
- (4) Cerebral infarction or cerebral hemorrhage confirmed by clinical and auxiliary examination is the only factor causing consciousness disorder, excluding other diseases caused consciousness disorder patients;
- (5) those aged between 18 and 85;
- (6) Family members or authorized principals know and sign informed consent;
- (7) did not enter other clinical studies at the same time.

#### **5.3 exclusion criteria:**

- (1) People with consciousness impairment mainly due to changes in consciousness content or special types;
- (2) confirmed carbon monoxide poisoning, brain tumor, brain trauma, brain parasitic disease, metabolic disorders;
- (3) Patients with severe primary diseases of liver, kidney, blood system, endocrine system and other diseases with poor prognosis, mental diseases;
- (4) have upper gastrointestinal hemorrhage, secondary epilepsy and other serious complications;
- (5) Those who have venous thrombosis and are currently on anticoagulant therapy;
- (6) patients judged by the investigator to be unsuitable for participation in this trial.

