## 1.research background

### 1.1 Post-stroke disturbance of consciousness

The development of emergency medicine and neuroscience has enabled more and more patients to survive after stroke, but a considerable number of severe patients remain with impaired consciousness.

1.1.1 The definition and classification of consciousness disorder: consciousness, including the level of consciousness and the content of consciousness. The normal level of consciousness is different from hyper alertness, wakefulness, sleepiness, light sleep, deep sleep, and dream. Awakening state refers to a physiological process of the human brain, which is a periodic alternating waking state with sleep, and depends on the integrity of the so-called "switch" system-the brain stem network structure ascending activation system. The content of consciousness, the so-called higher neural function activities, refers to the psychological processes (mental activities) such as human perception, thinking, memory, emotion and volitional activity, as well as the alertness of maintaining contact with the external environment through speech, hearing, vision, skilled movements and complex reactions. It is a function of the cerebral cortex, which depends on the integrity of the higher neural activities of the cerebral cortex .When the brain stem reticular structure ascending activation system is inhibited or the bilateral cerebral cortex is extensively damaged, the awakening state is weakened, the content of consciousness is reduced or changed, and the ability of the central nervous system to respond to internal and external environmental stimuli is reduced or disappeared, which can produce different degrees of consciousness disorders.

At present, the level of consciousness disorder is generally divided into: lethargy, lethargy and coma. According to the state of awakening, the content of consciousness and the evolution of the course of the loss of physical movement and the degree and breadth of brain function impairment, coma is usually divided into four stages: shallow coma: also called semi-coma, moderate coma, deep coma, excessive coma: also called irreversible coma or brain death. The common disorders of conscious content are: hazy state, hazy consciousness, delirium state,

waking coma. The common clinical types of waking coma are: de-cortical state, inactive silence, persistent vegetative state.

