8.1.2 Revised Coma Recovery Scale (CRS-R) : 0-23 points

The minimum state of consciousness (MCS) was assessed as: visual  $> 1$  or auditory  $> 2$  or verbal response  $> 2$  or motor  $> 2$  or communication  $> 0$  or arousal  $> 2$ ;

The evaluation criteria of persistent vegetative state (VS) were: vision  $\leq 1$  score, hearing  $\leq 2$  score, speech response  $\leq 2$  score, movement  $\leq 2$  score, communication = 0 score and arousal  $\leq 2$  score;

Clarity of mind was assessed on a scale of exercise = 6 points or communication = 2 points.

A change from below MCS to MCS, or from MCS to VS, or from VS to clear consciousness, or an increase of one level or more in the state of consciousness is considered valid.

8.2 Safety evaluation: Events such as needle dizziness, hematoma and unstable vital signs were recorded in the case report and reported to the trial designer. After group discussion, the case was withdrawn from the study. Follow-up of subjects after adverse events: in-hospital monitoring, 1 week after discharge, 4 weeks back to the hospital for re-examination.

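### The CRS-R responder rule in Section 8.1.2 has no scored level below vegetative state, so it gives comatose patients an excluded label, and it counts a fall from MCS to VS as success

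*Combined protocol and SAP*

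**What the plan says.** **Who is eligible.** Section 5.1(2) requires "Disturbance of consciousness dominated by altered degree of arousal". Section 5.3(1) excludes "People with consciousness impairment mainly due to changes in consciousness content or special types", and the summary table repeats that exclusion. Section 5.2(2) adds that "the GCS score was between 3 and 9".

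**How the protocol classifies the states.** Section 1.1.1 says "The common disorders of conscious content are: hazy state, hazy consciousness, delirium state" and ends that list with waking coma. It continues: "The common clinical types of waking coma are: de-cortical state, inactive silence, persistent vegetative state". Coma appears separately, among the levels of consciousness disorder. The same section later describes VS as a state in which some patients open their eyes, spontaneously or after stimulation, but lack perception and understanding.

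**How CRS-R response is scored.** Section 8.1.2 has three scored states. MCS needs any one subscale above its cut-off. For the lowest state, "The evaluation criteria of persistent vegetative state (VS) were" is followed by upper limits only: vision at most 1, hearing at most 2, speech at most 2, movement at most 2, communication 0, arousal at most 2. Clear consciousness is movement 6 or communication 2. The success rule is "A change from below MCS to MCS, or from MCS to VS, or from VS to clear consciousness", followed by "or an increase of one level or more in the state of consciousness is considered valid".

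**What is analysed.** GCS is the primary endpoint (Section 3.1) and CRS-R is secondary (Section 3.2, which does not say whether total or state). Section 13.3 analyses the consciousness scale score as mean and SD with univariate analysis of variance. It names no test for a CRS-R response rate and no baseline adjustment.

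**The concern.** The responder rule and the eligibility text use one term for two different things. Under Section 1.1.1, persistent VS is a content disorder, which Section 5.3(1) removes. Under Section 8.1.2, the same term covers every patient who meets no MCS criterion, including a patient in deep coma, whom Sections 5.1 and 5.2 admit.

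Two consequences follow for the response rate. Emergence from coma into VS produces no change of scored state, so it need not count. A patient who slips from MCS to VS is listed as a success. Both put patients in the wrong response category, and the second credits harm as benefit. A response rate built on this rule would be hard to interpret in either arm.

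**Working it through.** **Inputs.** Subscale ranges come from Section 1.1.3.1: auditory 0-4, visual 0-5, motor 0-6, speech 0-3, communication 0-2, arousal 0-3. State criteria and the success rule come from Section 8.1.2. The GCS response rule comes from Section 8.1.1.

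**Step 1: reproduce the plan's range.** 4 + 5 + 6 + 3 + 2 + 3 = 23, which agrees with the stated 0-23.

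**Step 2: classify every possible profile.** There are 5 × 6 × 7 × 4 × 3 × 4 = 10,080 subscale profiles. Where a profile meets both the clear and the MCS criteria, it is taken as clear.

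| State | Count | Range of totals |
|---|---|---|
| VS | 3 × 2 × 3 × 3 × 1 × 3 = 162 | 0 to 9 |
| Clear | 10,080 − (5 × 6 × 6 × 4 × 2 × 4) = 10,080 − 5,760 = 4,320 | 2 to 23 |
| MCS | 5,760 − 162 = 5,598 | 1 to 21 |

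These counts describe the rule, not patients.

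**Step 3: locate coma.** The all-zero profile satisfies every VS limit, so it is scored VS. The VS limits are the exact complement of the MCS criteria. As scored, being below MCS and being in VS are therefore the same set of 162 profiles, and no level lies beneath them.

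**Step 4: size of the uncounted gain.** The largest total still scored VS is 2 (auditory) + 1 (visual) + 2 (motor) + 2 (speech) + 0 (communication) + 2 (arousal) = 9. A rise from 0 to 9 of 23 can leave the state unchanged. This is the maximum the rule allows, not a typical loss.

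**Step 5: compare with the primary rule.** Suppose eye opening on GCS goes from 1 to 4 with the other items fixed, so the total goes from 4 to 7. Improvement = (7 − 4)/4 = 75%, which is effective under Section 8.1.1 (at least 20%). If the patient meets no MCS criterion, the CRS-R state is VS before and after, with no scored step.

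**Step 6: read the success rule literally.** From VS or MCS there are four possible changes of scored state.

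| Change | Direction | Counted? |
|---|---|---|
| VS to MCS | up | yes, as below MCS to MCS |
| VS to clear | up | yes, listed |
| MCS to clear | up | yes, only through the one-level clause |
| MCS to VS | down | yes, listed |

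Every change counts, including the decline. For example, visual 2 with all else 0 is MCS (total 2). Falling to all zeros is VS (total 0), and the rule as written calls that valid.

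**The case against.** The best defence has four parts.

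- **The lower rung may be implied.** The rule lists three steps, which suggests four rungs. If MCS and VS were transposed in drafting, it would run from below VS to VS, VS to MCS, and MCS to clear, and coma to VS would count. The one-level clause could be read the same way. This stands as far as intent goes: the rung is undefined and ambiguous rather than plainly ruled out. It does not rescue the rule, because no score marks that rung, and two assessors could not apply it reproducibly.
- **Coma to MCS is counted.** This stands. The gap is confined to gains that stay within the VS cut-offs.
- **The trial still sees the gain.** This stands. A rise in CRS-R score would appear in the score analysis of Section 13.3, and eye opening raises the primary GCS. No test is even named for the CRS-R response rate.
- **The classification comes from background text.** Section 1.1.1 is background, and Section 5.1(2) refers the diagnosis to a textbook that is not among the documents. That is a fair caution. However, Section 1.1.1 is the only place where the protocol says what a content disorder is.

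A reader might also infer that the eligibility criteria contradict each other, so that who enters depends on which text the screener follows. The documents do not support that. Sections 5.1(2) and 5.3(1) point the same way, Section 8.1.2 is an outcome rule, and the consciousness assessment listed for screening in Section 7.1 is GCS.

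**Conclusion.** The categorical CRS-R rule does not work as written. It labels comatose patients with a condition that Section 1.1.1, read with Section 5.3(1), excludes. It has no scored criterion separating coma from VS, so up to 9 of 23 points can be gained without a step. It also counts a decline from MCS to VS as valid.

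The reach is limited to a secondary responder rule. It would go too far to infer that recovery in the admitted patients is lost to the trial, or that the first stage of recovery is missed for the population as a whole. The primary GCS and the score analysis would register the gain, and GCS 3-9 with arousal-type disorders also admits patients who are not comatose, some of whom may already meet an MCS criterion. The proportion affected cannot be computed, because the documents give no baseline mix of coma, VS and MCS.

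This rests on three assumptions: Section 1.1.1 is the classification meant in Section 5.3(1), clear consciousness takes precedence over MCS when both are met, and the consciousness scale score in Section 13.3 includes CRS-R. The matter should be corrected, but it does not touch the primary endpoint.

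**What to change.** 1. Reconcile the terms in Sections 1.1.1, 5.1(2), 5.3(1) and 8.1.2, so that VS means the same in all four. The sponsor decides which states are meant to be eligible.
2. Restate the CRS-R ladder in ascending order with a scored level below VS, and count only upward moves. The sponsor chooses the cut-off for that level; the documents give no basis for one.
3. In Section 13.3, name the CRS-R total (0-23) at week 4, adjusted for baseline CRS-R (for example by analysis of covariance), as the secondary CRS-R analysis. Keep change of state as supportive. This improves on the unadjusted comparison now planned and does not depend on the ladder.

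The cost is protocol and SAP wording and a little analysis work. The test flow chart already has CRS-R at baseline, at weeks 1 to 4 and four weeks after discharge. Defining eligibility by CRS-R state is not needed. It would alter the schedule, since criteria are checked in the screening window and CRS-R is first scored at baseline.

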#### **5.4 Exit criteria**

Subjects withdrawing from the study for any reason are required to document their reasons, including, but not limited to, the following:

- 1) The subject withdraws the informed consent;
- 2) The sponsor terminates the study;
- 3) More serious adverse events affect participants' continued participation in the trial;
- 4) serious program violations/deviations;
- 5) pregnancy;

- 6) Poor compliance;
- 7) Loss of follow-up;
- 8) The investigator and/or sponsor considers that the subject's medical condition may endanger the subject's safety or that the continuation of the study will harm the subject's health;
- 9) Death;
- 10) Others.

### **5.5 Termination criteria**

Test termination criteria (if any of the following tests are met, the trial is terminated) :

- 1) Serious safety problems occur during the test;
- 2) Major errors in the clinical trial protocol are found in the trial;
- 3) The Ethics committee requests the termination of the trial.

### **6. Research treatment techniques:**

**6.1 Test instrument:** Tianxie brand 25mm× (25mm~40mm) millimeter needle produced by Suzhou Medical Supplies Factory Co., LTD.

**6.2 Non-research drugs:** common first-line drugs for the treatment of hypertension, such as amlodipine, nifedipine, nirendipine, metoprolol, valsartan, etc.; The commonly used first-line drugs for the treatment of diabetes such as metformin, acarbose, insulin aspartate, insulin glargine, etc.

### **6.3 Treatment methods:**

experimental group selected points: Baihui, Zhongwan, Guanyuan, Qihai, Tianshu (double); Point selection criteria: the national standard "Name and Location of points" (GB/T12346-2006). Intervention time: once a day, 5 days a week for 4 consecutive weeks. Twenty days in total;

Point selection of the control group: acupuncture treatment was performed 1cm beside the point selection of the experimental group.

**6.4 Intervention discontinuation Indicators:** Subjects will withdraw from the study if they have the following indications during treatment:

- (1) If the patient's condition deteriorates during treatment and there is a possibility

of dangerous events, the clinical observation of the case should be terminated according to the doctor's judgment;

(2) In the course of treatment, the patient's family members give up the clinical treatment halfway, request the doctor in charge to terminate the treatment, and terminate the clinical observation of the case;

(3) The treatment is effective, but the patient's family uses other treatment methods in order to speed up the therapeutic effect, and cannot determine the efficacy of the clinical study, and the clinical observation of the case is terminated.

**6.5 drug combination:** Information on all drug combinations during the study period (generic name, purpose of administration, dose, time of administration, etc.) must be recorded in detail in the case report form. Treatment with other investigational drugs is prohibited during the study period.

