### Test flow chart

| item                                 | Screening period |                  | Duration of treatment (weeks) |   |   |   | Four weeks after discharge | Quit |
|--------------------------------------|------------------|------------------|-------------------------------|---|---|---|----------------------------|------|
|                                      | 4week s~2days    | base line /-1day | 1                             | 2 | 3 | 4 | Phone or video follow-up   |      |
| Informed consent                     | X                |                  |                               |   |   |   |                            |      |
| Demography                           | X                |                  |                               |   |   |   |                            |      |
| Inclusion/exclusion criteria         | X                |                  |                               |   |   |   |                            |      |
| Medical history                      | X                |                  |                               |   |   |   |                            |      |
| CRS-R scale                          |                  | X                | X                             | X | X | X | X                          |      |
| GCS score                            |                  | X                | X                             | X | X | X | X                          |      |
| NIHSS score                          |                  | X                | X                             | X | X | X | X                          |      |
| FOUR score                           |                  | X                | X                             | X | X | X | X                          |      |
| Electroencephalogram                 |                  | X                |                               |   |   | X |                            |      |
| brainstem auditory evoked potentials |                  | X                |                               |   |   |   | X                          |      |
| encephalofluctuograph                |                  | X                |                               |   |   |   | X                          |      |

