### **4.2.2 Blind state/broken blind**

Because of the particularity of acupuncture treatment, it is impossible to implement double blindness, so this study implemented single blindness. The realization of single blind conditions: false acupoint method, and Tongyuan acupuncture method are adopted acupuncture methods so that patients and family members do not know the grouping. Moreover, trial designers, scale evaluators, acupuncture operators, and data statisticians do not know the status of treatment groups of individual subjects.

Blindness is crucial to the integrity of this clinical study. However, in the event

of a medical emergency or pregnancy event in an individual subject, the information about the study treatment received by the subject is so important to the subject's management that the treating physician will need to de-blind the subject.

Before blinding a subject's treatment, the investigator should determine that this information is necessary, that it will change the subject's immediate treatment. In many cases, especially when the subject's emergency condition is clearly unrelated to the study protocol, it can be assumed that the subject is being treated with the active drug without the need for blind treatment.

The need for blindness should first be discussed with the responsible medical monitor before determining the best response.

After unblinding, the subjects will withdraw from the study and terminate treatment. Safety follow-up and survival follow-up are still required.

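### Section 6.4 ends observation of patients partly because of their course, no week-4 GCS is scheduled after withdrawal, and the analysis has no rule for missing scores or death; the two FAS definitions also conflict

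*Combined protocol and SAP*

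**What the plan says.** **Who leaves.** Section 6.4 is headed as a rule for discontinuing the intervention, but its opening line goes further: "Subjects will withdraw from the study if they have the following indications during treatment". It has three items.
- Item 1, deterioration with possible danger: "the clinical observation of the case should be terminated according to the doctor's judgment".
- Item 2, the family gives up treatment; observation ends.
- Item 3, treatment is working but the family adds other treatment, so that one "cannot determine the efficacy of the clinical study, and the clinical observation of the case is terminated".

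Section 8.2 adds events such as hematoma: "After group discussion, the case was withdrawn from the study". Section 4.2.2 adds unblinding: "After unblinding, the subjects will withdraw from the study and terminate treatment. Safety follow-up and survival follow-up are still required". Section 5.4 lists further exits, including death, poor compliance and loss to follow-up, and requires only a reason: "Subjects withdrawing from the study for any reason are required to document their reasons".

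**What is measured afterwards.** After unblinding, safety and survival. After an adverse event, "in-hospital monitoring, 1 week after discharge, 4 weeks back to the hospital for re-examination", with no scale named. Section 4 attaches a consciousness scale to the contact 4 weeks after discharge, which is not week 4 of treatment. The flow chart's header ends "Four weeks after discharge | Quit", and as extracted nothing is marked in the last column.

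**What is analysed.** GCS is the primary endpoint (3.1), and 4 weeks of treatment is a named evaluation time (8.1). Sections 13.3 and 13.4 compare the groups at each time point by ANOVA. No rule covers missing scores, withdrawal or death. The Summary's FAS requires randomisation, one intervention and a baseline. The FAS in 13.2 requires one treatment and at least one effectiveness evaluation.

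**The concern.** Deterioration and improvement are what GCS measures. A rule that ends observation partly on those grounds makes the missing week-4 scores depend on the outcome. The analysis then compares the patients who remain, and randomisation no longer guarantees that those two groups are alike.

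If needling changes nothing and the blinding described in 4.2.2 holds, the same kinds of patients leave both arms and no bias is expected. If needling works, even one rule applied blindly removes different shares of each arm, because the arms then contain different numbers of deteriorating and improving patients. The estimated effect can shift either way.

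The FAS conflict is a separate defect. A patient treated once and withdrawn before any effectiveness evaluation is in the Summary's FAS and outside the one in 13.2. Neither definition supplies a week-4 score.

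**Working it through.** **1. The plan's own figure.** Inputs from 13.1: rates 79.4% and 54.8%, U values 1.96 and 1.28, 15% shedding. Pooled P = (0.794 + 0.548)/2 = 0.671.

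n = 2 × (1.96 + 1.28)² × 0.671 × 0.329 / 0.246² = 76.6 per group, against a stated 76. Then 76 × 1.15 = 87.4, the stated 87. Losing 15% at random leaves 87 × 0.85 ≈ 74 per arm, with power of about 90% for a two-proportion test. The allowance therefore covers lost numbers. It does not cover selective loss.

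**2. Does any section recover a week-4 GCS?**

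| Route out | Follow-up named | Week-4 GCS named? |
|---|---|---|
| 6.4 items 1 to 3 | none; observation ends | no |
| 4.2.2 unblinding | safety, survival | no |
| 8.2 adverse event | re-examination | no |
| 5.4 other exits | reason recorded | no |

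Scores already taken at weeks 1 to 3 enter the comparisons at those weeks, but not the one at week 4.

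**3. Design effect true, one rule in both arms.** Assumption: a share a of non-responders and a share b of responders is removed, the same in each arm, with 15% leaving overall. The observed rate is p(1−b) / [p(1−b) + (1−p)(1−a)].
- All leavers non-responders: a = 0.15/0.329 = 0.456, b = 0. Rates 0.794/0.906 = 87.6% and 0.548/0.794 = 69.0%. Difference 18.6 points; 9.4% and 20.6% of the arms are removed.
- 75% non-responders: a = 0.1125/0.329 = 0.342, b = 0.0375/0.671 = 0.056. Rates 84.7% and 63.5%. Difference 21.2 points.
- All responders: a = 0, b = 0.15/0.671 = 0.224. Rates 75.0% and 48.5%. Difference 26.5 points.

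The true difference in each case is 24.6 points.

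**4. No true effect, 54.8% in both arms.** Assumption: a share r of an arm leaves, and a share f of its leavers are non-responders. Observed rate = [0.548 − r(1−f)]/(1−r).
- Same r and same f in both arms: no shift.
- r = 15% v 5%, f = 1: 0.548/0.85 = 64.5% v 0.548/0.95 = 57.7%, a shift of 6.8 points.
- r = 15% in both, f = 0.75 v 0.25: 0.5105/0.85 = 60.1% v 0.4355/0.85 = 51.2%, a shift of 8.8 points before rounding. Equal numbers leaving is therefore not a safeguard in itself.

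In simulation with 87 per arm, a two-proportion test rejected in about 14% and 19% of trials under the last two patterns, against 5.7% with no removal. Sections 13.3 and 13.4 do not specify that test. On the planned ANOVA of week-4 GCS (assumed mean 9, SD 2 to 3), the patterns tried gave about 6% to 18%, depending on the pattern and on how removal was modelled.

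**5. Outer limits.** Suppose 15% per arm are unobserved and the observed rates are 79.4% and 54.8%. The difference among all randomised patients then lies between 0.85 × 0.794 − (0.85 × 0.548 + 0.15) = 5.9 points and (0.85 × 0.794 + 0.15) − 0.85 × 0.548 = 35.9 points.

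**The case against.** Several points on the other side have force.

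- A reader might infer that 6.4 removes patients simply because of their course. It does not. Item 2 is a family decision that may or may not reflect the course, and item 3 needs added treatment as well as improvement. Improvement alone removes nobody.
- A reader might infer that the plan restricts the week-4 analysis to those who stayed. No section says so; that is the default result of ending observation and giving no other rule. Section 8.1 could be read as asking for a score when the intervention ends, the effective rate in 8.1.1 uses a post-treatment score with no week named, and 13.1 says that shed cases were not excluded. These wordings are ambiguous, and none schedules a week-4 score after withdrawal or can replace one that was never taken.
- The empty exit column is weak evidence. In the same extracted chart, the evoked potentials and encephalofluctuograph are marked at the contact after discharge, whereas 7.2 places them at week 4 of treatment. Marks may have moved, so the point does not rest on that column.
- A reader might infer that the plan invites a false positive. The documents do not show this. Every inflated error rate above needs arms that differ in who leaves, and no section shows such a difference.
- If the family's decision under item 2 also withdraws consent to follow-up, continued scoring may recover little for those patients.

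**Conclusion.** The point holds as a defect in how outcomes are kept and analysed. Study withdrawal is tied in part to the patient's course, no week-4 GCS is scheduled after it, and nothing states how missing scores or deaths enter the ANOVA. The conflict between the FAS definitions stands beside it.

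Size and direction cannot be computed from the documents. If the design rates are true and 15% leave under one rule, the illustrated range is 18.6 to 26.5 points against a true 24.6. Most of that range is a shrinkage of the effect; the largest inflation shown is 1.9 points. With no true effect and the same number and kind of patients leaving each arm, there is no shift. All leaving patterns, and the GCS mean and SD, are assumptions. The plan should be changed because a score not taken cannot be recovered at analysis. Confidence is medium.

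**What to change.** Leave the rules for stopping treatment as they are.

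1. In 4.2.2, 5.4, 6.4 and 8.2, separate stopping treatment from stopping observation. Keep scoring GCS and CRS-R at the scheduled weeks, including week 4, unless consent to follow-up is withdrawn.
2. Use one FAS in the Summary and in 13.2: all randomised patients, analysed as randomised. Name it as primary.
3. Prespecify a week-4 analysis that uses all scheduled scores and adjusts for baseline GCS. State how death is handled in that primary analysis itself and do not leave it as ordinary missing data. Examples are worst rank, which makes the comparison rank-based, or ineffective if the effective rate is tested. Giving deaths a score of 3 would not do, because a patient enrolled at GCS 3 would count as unchanged. Add a tipping-point sensitivity analysis for other withdrawals left unscored.
4. State that cases added in 2025 (Summary and 14.4) do not replace patients who left, who stay in the analysis.

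**Cost.** Protocol wording, different analysis procedures, and some in-person scores for patients who stopped early: at most about 0.15 × 174 = 26 patients at the plan's shedding rate. The telephone or video contact after discharge falls at another time and cannot replace them.

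**Downsides to disclose.** Patients with little treatment may dilute the effect. Scores after family-added treatment include its effect, which is the reason 6.4 gives for ending observation, so report that treatment by arm and keep the PPS as support.
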